6.10.1. Primary Outcome and Methodology

Primary outcome PASI 90 and its analysis are described in [Table AMAK.6.5](#) and [Table AMAK.6.6](#). The primary analysis is a CMH analysis with NRI.

6.10.2. Additional Analyses of the Primary Outcome

Additional analyses of the primary outcome are described in [Table AMAK.6.5](#) and [Table AMAK.6.6](#).

6.10.3. Multiple Testing Controlled Secondary Efficacy Analyses

Secondary outcomes and their analyses are described in [Table AMAK.6.5](#) and [Table AMAK.6.6](#). The primary analysis for all multiple testing controlled secondary efficacy analyses is a CMH analysis with NRI.

6.10.4. Other Secondary Efficacy Analyses

Other secondary analyses of efficacy are described in [Table AMAK.6.5](#) and [Table AMAK.6.6](#).

6.10.5. Sensitivity Analyses

Sensitivity analyses are described in [Table AMAK.6.5](#) and [Table AMAK.6.6](#).

6.11. Health Outcomes/Quality-of-Life Analyses

See [Table AMAK.6.5](#) and [Table AMAK.6.6](#).

6.12. Bioanalytical and Pharmacokinetic/Pharmacodynamic Methods

Details of pharmacokinetic/pharmacodynamic (PK/PD) analyses can be found in a separate PK/PD analysis plan.

6.13. Safety Analyses

[figure not shown]
The planned analyses of safety data will be performed with an intent to maintain consistency with compound level safety standards. These standards are based on internal standards which were informed by Clinical Data Interchange Standards Consortium (CDISC) standards, regulatory guidance (e.g., Food and Drug Administration [FDA] Clinical Review Template), and cross-industry standardization efforts (e.g., Pharmaceutical Users Software Exchange [PhUSE] white papers from the Standard Analyses and Code Sharing Working Group provided in the PhUSE Computational Science Deliverables Catalog [WWW]).

All safety evaluations will be based upon the following safety analysis populations with their associated study periods:

- Induction Safety Population
- Re-randomized Maintenance Safety Population
- All Miri Safety Population

These analysis populations are fully defined in [Table AMAK.6.1](#), while [Table AMAK.6.2](#) describes the treatment groups, associated study periods and the comparisons for each analysis

population. Figure AMAK.6.2 gives a graphical depiction of each of the 3 safety populations along with the treatment groups, associated study periods and the comparisons for each analysis population.

Abbreviations: LV = last study visit; miri = mirikizumab; Q4W = administration once every 4 weeks; Q8W = administration once every 8 weeks; V = visit; w = weeks; W = week.

* Option to enter Study AMAH or to enter the Post-Treatment Follow-Up Period.

a Patients may receive placebo injections during the Maintenance Period to maintain the study blind across treatment groups.

b Patients who relapse during the Maintenance Period will be treated with 250 mg mirikizumab for the remainder of the study and will be monitored for recapture of efficacy response,

c First Maintenance Period dosing at Week 16.

Figure AMAK.6.2. Illustration of safety populations within the study design.

Unless otherwise noted, Fisher’s exact test will primarily be used to compare percentages, and odds ratios will be provided. Odds ratios will be created with mirikizumab treatment as the numerator and placebo as the denominator.

Treatment differences in mean change for continuous measurements will be assessed using an analysis of covariance (ANCOVA) model containing terms for treatment and the continuous covariate of baseline measurement. Type 3 sums of squares will be used. The significance of

within-treatment group changes from baseline will be evaluated by testing whether the treatment group LSMeans changes from baseline are different from zero using a t-statistic.

Not all displays described in this section will necessarily be included in the CSRs. Any display described and not provided in the CSR would be available upon request. Not all displays will necessarily be created as a “static” display. Some may be incorporated into interactive display tools instead of or in addition to a static display. Any display created interactively will be included in the CSR if deemed relevant to the discussion.

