10.3.4. Safety Analyses

Safety assessments will include AEs, SAEs, AESIs, laboratory analytes, vital signs, QIDS-SR16, and C-SSRS.

The Induction Period safety analyses will compare mirikizumab to placebo using the methods described in Section 10.3.1. The Maintenance Period safety analyses will summarize safety measures by treatment.

Adverse events will be coded according to the *Medical Dictionary for Regulatory Activities* (MedDRA) and summarized by system organ class, preferred term, severity, and relationship to investigational product. A treatment-emergent adverse event (TEAE) is defined as an event that first occurred or worsened in severity after baseline. For each event classification term, the number of patients experiencing a TEAE with that classification term will be tabulated.

Treatment-related TEAEs are defined as events that are indicated by the investigator on the eCRF to be related to treatment. If a patient reports the occurrence of a particular event more than once, the most severe of those events will be included in the summary tables of TEAEs, and the most severe of the most related of those events will be included in the summary tables of treatment-related events. For events that are gender specific, the denominator and computation of the percentage will only include patients from the given gender.

Adverse events of special interest are defined in Section 9.2.3 and the analysis plan will be described in the Program Safety Analysis Plan and SAP.

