5.1. Determination of Sample Size

Approximately 500 patients will be randomized at a 4:1 ratio in the blinded Induction Period to receive 250 mg mirikizumab or placebo SC at Weeks 0, 4, 8, and 12. Stratified block randomization will be performed with the following stratification factors: previous exposure to biologic therapy (yes/no), body weight (<100 kg or ≥100 kg), and geographic region (North America or Other).

There are multiple primary endpoints in this study: static Physician’s Global Assessment (sPGA) (0,1) and PASI 90 at Week 16. The assumed sPGA (0,1) responses are 70% for the mirikizumab arm and 5% for the placebo arm. The assumed PASI 90 responses are 70% for the mirikizumab arm and 3% for the placebo arm. These assumptions are based upon the results of

the mirikizumab Phase 2 Study AMAF (Reich et al. 2017) and review of historical clinical studies in psoriasis (Langley et al. 2014; Gordon et al. 2016; Blauvelt et al. 2017; Papp et al. 2017; Reich et al. 2017).

With a total sample size of 500 patients, randomizing 400 patients to the mirikizumab arm and 100 patients to the placebo arm, this study has power of >95% for testing superiority of mirikizumab to placebo based on a 2-sided chi-square test with alpha of 5% on sPGA(0,1). It also provides a power of >95% for testing superiority of mirikizumab to placebo on PASI 90 based on a 2-sided chi-square test with alpha of 5%.

In order to account for multiple testing for the comparisons of 2 mirikizumab groups against the placebo group in the Maintenance Period, a 2-sided chi-square test at the 0.025 level is assumed. Assuming 70% of the mirikizumab patients are re-randomized in the Maintenance Period at Week 16 (Visit 7) at a 1:1:1 ratio to 250 mg mirikizumab Q8W, 125 mg mirikizumab Q8W or placebo, approximately 93 patients will be included in each treatment group. Stratified block randomization will be performed with the stratification factor of body weight at baseline (<100 kg or \geq 100 kg). This sample size will provide >95% power to test the difference in the proportion of patients maintaining PASI 90 from Week 16 (Visit 7) after re-randomization at the start of the Maintenance Dosing Period to Week 52 (Visit 16) between each mirikizumab dosing interval and placebo, assuming the proportions of patients maintaining PASI 90 are 80% for 250 mg mirikizumab Q8W, 70% for 125 mg mirikizumab Q8W, and 10% for placebo.

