6.13.2. Adverse Events

A treatment-emergent adverse event (TEAE) is defined as an event that first occurred or worsened in severity after baseline. The MedDRA Lowest Level Term (LLT) will be used in the treatment-emergent computation. The maximum severity for each LLT during the baseline period will be used as baseline. The treatment period will be included as postbaseline for the analysis. For events with a missing severity during the baseline period, it will be treated as “mild” in severity for determining treatment-emergence. Events with a missing severity during the postbaseline period will be treated as “severe” and treatment-emergence will be determined by comparing to baseline severity. For events occurring on the day of first taking study medication, the start times of the study treatment and AE will be used to determine whether the event was pre- versus post-treatment. If start time for the AE is missing, it will be assumed to have started in the later period.

Summary tables as described in [Table AMAK.6.7](#) will be presented for the three safety populations/ periods, as indicated. Summary tables will include the number and percentage of patients reporting an event. For events that are gender-specific (as defined by MedDRA), the number of participants at risk will include only patients from the given gender. Comparisons will be performed using Fisher’s exact test. P-values should be interpreted cautiously due to the fact that multiplicity is not controlled.

For the three safety populations, the baseline period and postbaseline periods (see [Figure AMAK.6.2](#)) will be defined as follows:

- *Induction Safety Population*: The baseline period is the Screening Period. The postbaseline period will be the Induction Period.
- *Re-randomized Maintenance Safety Population*: The baseline events are those events which are ongoing at the start of the Maintenance Period (i.e., the baseline period is a moment in time). The postbaseline period is defined as the Maintenance period.
- *All Miri Safety Population*: The baseline period for patients randomized to mirikizumab during induction is the screening period. For all other patients, the baseline events are those events which are ongoing at the time of first injection with mirikizumab. Three different postbaseline periods will be used:

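### SAP 6.13 names a Fisher p-value and an odds ratio for the Induction safety comparison but no risk difference or confidence interval, and for uncommon events the odds ratio often has no finite value

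*SAP*

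**What the plan says.** SAP 6.13 sets the default for categorical safety data: Fisher's "exact test will primarily be used to compare percentages, and odds ratios will be provided". It fixes the direction of the ratio: "Odds ratios will be created with mirikizumab treatment as the numerator and placebo as the denominator". Protocol 10.3.1 also names Fisher's exact test and sets two-sided alpha of 0.05 as the general default. Protocol 10.3.4 states: "The Induction Period safety analyses will compare mirikizumab to placebo using the methods described in Section 10.3.1".

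SAP 6.13.2 plans counts and percentages of patients with each event and adds one caution: "P-values should be interpreted cautiously due to the fact that multiplicity is not controlled".

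The arm sizes come from SAP 5.1: "randomizing 400 patients to the mirikizumab arm and 100 patients to the placebo arm". That section gives power for efficacy only. Neither document gives a power or precision figure for safety, or any expected adverse event rate.

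For binary efficacy endpoints, SAP 6.1.4 plans a stratified common risk difference with a 95% confidence interval. No equivalent appears in the visible safety sections.

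**The concern.** Induction is the trial's only randomized comparison of drug with placebo in which no placebo patient has yet had drug; everyone on placebo in the re-randomized Maintenance comparison has already had mirikizumab. It is therefore the cleanest safety contrast the study offers, and it rests on 100 placebo patients.

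Two things follow. First, the named effect measure divides by the placebo odds, so it has no finite value when placebo has no events. That can be expected for rare adverse events of special interest and for preferred terms near the 1% display cut in SAP 6.13.2.1. Second, a small control arm makes a missed difference likely when the true excess is modest. The only caution in the SAP concerns multiplicity, which guards against false positives. Nothing alerts the reader to the opposite error, and no planned column shows how large an excess the data leave open.

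**Working it through.** **Inputs.** 400 and 100 patients (SAP 5.1). The Induction Safety population is randomized patients with at least one dose (SAP Table AMAK.6.1), so about these numbers. Alpha is 0.05, two-sided (Protocol 10.3.1). All adverse event rates below are assumptions, shown as a range.

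**1. The plan's own power figure.** "The assumed sPGA (0,1) responses are 70% for the mirikizumab arm and 5% for the placebo arm", and "The assumed PASI 90 responses are 70% for the mirikizumab arm and 3% for the placebo arm". For sPGA (0,1) the pooled rate is (400×0.70 + 100×0.05)/500 = 0.57.
- SE under the null = √[0.57×0.43×(1/400 + 1/100)] = 0.0554
- SE under the alternative = √[0.70×0.30/400 + 0.05×0.95/100] = 0.0316
- z = (0.65 − 1.96×0.0554)/0.0316 ≈ 17.1, so power exceeds 99.9%

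PASI 90 gives the same result. The stated figure of more than 95% is reproduced, but it concerns differences of 65 to 67 percentage points and says nothing about safety.

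**2. How often the odds ratio has no finite value.** P(no placebo event) = (1 − p)^100, where p is the placebo incidence.

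| p | P(no placebo event) |
|---|---|
| 0.5% | 61% |
| 1% | 37% |
| 2% | 13% |
| 5% | 0.6% |

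**3. Fisher power at 400 versus 100.** All outcomes of the two binomials were enumerated, and rejections at p ≤ 0.05 in the direction of harm were summed.

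| Placebo | Mirikizumab | Power |
|---|---|---|
| 1% | 3% | 6% |
| 2% | 4% | 8% |
| 2% | 6% | 31% |
| 5% | 10% | 30% |
| 10% | 20% | 66% |
| 5% | 15% | 82% |
| 2% | 10% | 83% |
| 1% | 8% | 85% |

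**4. Count needed for p ≤ 0.05.** With no placebo events, 14/400 gives p = 0.084, 15/400 gives 0.0499 and 16/400 gives 0.051 (the exact p-value is not monotone in the count). At least 15/400 (3.75%) are therefore needed. With one placebo event, 24/400 (6%) are needed.

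**5. What an interval adds.** Take 12/400 versus 0/100. The Fisher p-value is 0.14 and the odds ratio is not finite. The Wilson limits are 1.72% to 5.17% for 12/400 and 0% to 3.70% for 0/100. The Newcombe limits for the risk difference of 3.0% are:
- lower: 3.0 − √[(3.0 − 1.72)² + (3.70 − 0)²] = −0.9%
- upper: 3.0 + √[(5.17 − 3.0)² + (0 − 0)²] = 5.2%

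For 40/400 versus 5/100, p = 0.17 and the odds ratio is 2.1. The risk difference is 5.0% (−1.7% to 9.4%). In both cases p exceeds 0.05 while excesses of about 5 and 9 points remain compatible with the data.

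**The case against.** The strongest answer is that the safety output is much richer than a p-value and a ratio. Counts and percentages by arm are planned, as are tables by maximum severity, serious event and death listings, laboratory shift tables, hepatic threshold percentages and adjudicated cerebro-cardiovascular events. Anyone with the counts can compute a risk difference and its interval. This stands. A reader might infer that the p-value would be the only comparative figure left, and the documents do not support that.

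A reader might also infer that the plan treats p > 0.05 as absence of a signal. No passage says so; the SAP asks for caution with p-values, and an external data monitoring committee reviews unblinded safety data.

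Nor is it supportable that the comparison would miss most relevant harms. Power depends on assumed rates and reaches 82% to 85% for the larger excesses above, and no document defines which harms are relevant. The odds ratio problem is confined to uncommon events.

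Another point stands in part. SAP 6.13 and 6.13.8 defer to compound level safety standards, Protocol 10.3.4 refers to a Program Safety Analysis Plan, and the injection site section is redacted. An interval could be specified in any of these. The absence is therefore of the visible text only. Even so, SAP 6.13 itself names the odds ratio and could as easily name, or point to, an interval.

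Finally, the low power comes from the size of the placebo arm, and an interval does not cure it. That is true. The case for the interval is that it shows the limitation in the table where the comparison is read.

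**Conclusion.** The point holds as a reporting gap. In the visible text, the Induction Safety comparison has a test and an odds ratio but no risk difference, confidence interval or zero-cell rule, while binary efficacy in the same SAP has a risk difference with an interval.

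The gap matters most for events at or below about 1% incidence, where the chance that the odds ratio has no finite value is 37% or more, and for modest excesses, where Fisher power is 6% to 31% for the pairs between 1% versus 3% and 5% versus 10%. It matters little for the odds ratio at 5% incidence or above, and the test performs adequately for large excesses.

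These figures assume 400 and 100 dosed patients and the event rates shown. The conclusion about the missing interval does not depend on the rates, but it would fall away if the compound level safety standards already require one. No primary or multiplicity-controlled conclusion is affected.

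**What to change.** In SAP 6.13, for the Induction Safety population:

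- Report the risk difference (mirikizumab minus placebo) with a 95% Newcombe or Miettinen-Nurminen interval beside the Fisher p-value for treatment-emergent adverse events, serious adverse events, adverse events of special interest and treatment-emergent laboratory shifts. If the compound level safety standards already require this, cite them instead.
- Show the odds ratio only when both arms have events.
- After the multiplicity caution in SAP 6.13.2, add that a non-significant p-value is not evidence of no difference.

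The cost is SAP wording and one more column in existing tables, with no new data. The downside is that wide intervals will make plain how little 100 placebo patients can exclude; they show the limited precision but do not raise power.

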6.13.1. Extent of Exposure

Duration of exposure to study treatment will be summarized by treatment group for each of the three safety analysis populations (i.e., Induction Safety, Re-randomized Maintenance Safety, and All Miri Safety). For the treatment period of interest associated with each safety analysis population, exposure will be calculated as the time period length in years (see Section 6.1.2) with start and end dates described in Table AMAK.6.3. The following periods will be used for calculations:

- For the Induction Safety Population, the Induction Period Interval will be used.
- For the Re-randomized Maintenance Safety Population, the Maintenance Period Interval will be used. As noted in Table AMAK.6.3, patients who relapse after re-randomization during the maintenance period are considered to have left the maintenance period and entered the relapse period.
- For the All Miri Safety Population, we calculate the exposure for 3 different period definitions:
 - Exposure for “all miri” will be calculated by finding the length of the “All Miri Period.” For patients who are re-randomized to placebo, the “All Miri Period” may be composed of two non-overlapping periods of time, and the length of the two periods of time will be summed.
 - Exposure for “all miri + placebo withdrawal” will be calculated as the length of the “All Miri + Placebo Withdrawal Period.”
 - Exposure for “all miri + placebo withdrawal + follow-up (FUP)” will be calculated as the length of the “All Miri + placebo withdrawal + FUP Period.”

Total patient-years (PY) of exposure will be reported for each of the three safety analysis populations by treatment group (see Table AMAK.6.2). Descriptive statistics will be provided for patient-weeks of exposure and the frequency of patients falling into different exposure ranges will be summarized:

- >0; ≥4 weeks; ≥8 weeks; ≥12 weeks; ≥16 weeks; ≥24 weeks; ≥32 weeks; ≥40 weeks; and ≥48 weeks
- >0 to <4 weeks; ≥4 weeks to <8 weeks; ≥8 weeks to <12 weeks; ≥12 weeks to <16; ...; ≥48 weeks

Additional exposure ranges may be considered, if necessary. No p-values will be reported in these tables as they are intended to describe the study populations, rather than test hypotheses about them.

6.13.2. Adverse Events

A treatment-emergent adverse event (TEAE) is defined as an event that first occurred or worsened in severity after baseline. The MedDRA Lowest Level Term (LLT) will be used in the treatment-emergent computation. The maximum severity for each LLT during the baseline period will be used as baseline. The treatment period will be included as postbaseline for the analysis. For events with a missing severity during the baseline period, it will be treated as “mild” in severity for determining treatment-emergence. Events with a missing severity during the postbaseline period will be treated as “severe” and treatment-emergence will be determined by comparing to baseline severity. For events occurring on the day of first taking study medication, the start times of the study treatment and AE will be used to determine whether the event was pre- versus post-treatment. If start time for the AE is missing, it will be assumed to have started in the later period.

Summary tables as described in [Table AMAK.6.7](#) will be presented for the three safety populations/ periods, as indicated. Summary tables will include the number and percentage of patients reporting an event. For events that are gender-specific (as defined by MedDRA), the number of participants at risk will include only patients from the given gender. Comparisons will be performed using Fisher’s exact test. P-values should be interpreted cautiously due to the fact that multiplicity is not controlled.

For the three safety populations, the baseline period and postbaseline periods (see [Figure AMAK.6.2](#)) will be defined as follows:

- *Induction Safety Population*: The baseline period is the Screening Period. The postbaseline period will be the Induction Period.
- *Re-randomized Maintenance Safety Population*: The baseline events are those events which are ongoing at the start of the Maintenance Period (i.e., the baseline period is a moment in time). The postbaseline period is defined as the Maintenance period.
- *All Miri Safety Population*: The baseline period for patients randomized to mirikizumab during induction is the screening period. For all other patients, the baseline events are those events which are ongoing at the time of first injection with mirikizumab. Three different postbaseline periods will be used:
 - For “all miri,” the “All Miri Period” will be used. Note that the “All Miri Period” excludes events that began during the “Placebo Withdrawal Period” for patients who were re-randomized to Placebo.
 - For “all miri + placebo withdrawal,” the “All Miri + Placebo Withdrawal Period” will be used.
 - For “all miri + placebo withdrawal + FUP,” the “All Miri + Placebo Withdrawal + FUP Period” will be used.

Table AMAK.6.7. Summary Tables Related to Adverse Events

Analysis	Population/ Period ^a
Overview of AEs	I; R; A
Summary of TEAE PTs by decreasing frequency	I; R; A
Summary of TEAE PTs occurring in $\geq 1\%$ of patients by decreasing frequency	I; R
Summary of TEAE PTs by decreasing frequency within SOC	I; R
Summary of TEAE PTs by maximum severity by decreasing frequency within SOC	I; R
Summary of SAE PTs by decreasing frequency	I; R; A
Summary of AEs leading to study discontinuation	I; R; A
Listing of SAEs	I
Listing of Deaths	All Entered patients

Abbreviations: AEs = adverse event; PTs = Preferred Terms; SAE = serious adverse event; SOC = System Organ Class; TEAE = treatment-emergent adverse event.

^a Populations are abbreviated as follows: I = Induction Safety; R = Re-randomized Maintenance Safety; A = All Miri Safety.

